720 mg	0.751	0.169	0.080	0.154	0.176	0.027	0.100	0.844

The prior may be updated once the trial has started in case new data that can be used will be available. The prior that is used for each BLRM analysis for the SMC meetings will be documented in the SMC minutes, the prior used for the final analysis will be documented in the Trial Statistical Analysis Plan (TSAP).

7.1.2 Statistical design – Part II (BI 836880 and BI 754091 combination dose finding)

Part II of the trial will be performed as an open label single arm study. The primary objective of the design is also to determine the MTD in Japanese patients of BI 836880 in combination with BI 754091. To determine the MTD, patients are entered sequentially into escalating dose cohorts. The dose-finding will be guided by a Bayesian 5-parameter logistic regression model with overdose control. The model is defined as follows. Let $\pi_{1,d1}$ be the probability of having a DLT when giving dose d_1 of BI 836880 as monotherapy, and $\pi_{2,d2}$ the probability of having a DLT when giving dose d_2 of the combination partner BI 754091 as monotherapy, respectively. A logistic regression model is used to model the dose-toxicity relationship for each component individually:

BI 836880 part:

$$\text{logit}(\pi_{1,d1}) = \log(\alpha_1) + \beta_1 \log(d_1/d_1^*)$$

BI 754091 part:

$$\text{logit}(\pi_{2,d2}) = \log(\alpha_2) + \beta_2 \log(d_2/d_2^*)$$

where $\text{logit}(\pi) = \log(\pi / (1 - \pi))$, the reference doses $d_1^* = 500 \text{ mg}$ and $d_2^* = 240 \text{ mg}$ are set for BI 836880 and BI 754091, respectively.

Assuming no toxicity interaction between the two compounds, the probability of a DLT when giving the combination of dose d_1, d_2 is obtained as

$$\pi_{12,d1,d2}^0 = \pi_{1,d1} + \pi_{2,d2} - \pi_{1,d1}\pi_{2,d2}$$

with corresponding odds

$$\text{odds}(\pi_{12,d1,d2}^0) = \pi_{12,d1,d2}^0 / (1 - \pi_{12,d1,d2}^0)$$

In order to account for a potential positive (higher toxicity than expected under independence) or negative (lower toxicity than expected under independence) interaction between BI 836880 and BI 754091, a dose-dependent interaction term $-\infty < \eta < \infty$ is introduced to the model by the following definition:

$$\text{odds}(\pi_{12,d1,d2}) = \text{odds}(\pi_{12,d1,d2}^0) \exp(\eta d_1/d_1^* d_2/d_2^*)$$

and $\pi_{12,d1,d2}$ is used in the likelihood

$$r_{d1,d2} \sim \text{Binomial}(n_{d1,d2}, \pi_{12,d1,d2})$$

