To determine the prior distributions for θ_1 , θ_2 and η a meta-analytic predictive (MAP) approach will be used. Toxicity information on BI 836880 monotherapy from the study 1336-0001, and the Part 1 of this study, toxicity information on BI 754091 monotherapy from the studies 1381-0001 and 1381-0004, and toxicity information on the combination of BI 836880 and BI 754091 from study 1336-0011 will be incorporated. Exact details on the evaluation of the model using hypothetical data scenarios and operating characteristics are provided in the statistical appendix; a brief description is given here.

The historical data for BI 836880 can be found in [Table 7.1.1: 1](#). For BI 754091, the historical data can be found in Tables [7.1.2: 2](#) and [7.1.2: 3](#). Expected historical data for the combination of BI 836880 and BI 754091 can be found in [Table 7.1.2: 4](#). Since data from 1336-0012 Part 1 and 1336-0011 were not yet available by the time of finalization of the CTP, data as is might be observed in future in these trials will be used as dummy data. This dummy data will be replaced by actual data as soon as it becomes available. Whenever BLRM calculations are performed for Part 2 of 1336-0012, all available information will be used and the resulting prior distribution will be documented.

Table 7.1.2: 1 Hypothetical data expected from 1336-0012 part 1

Dose BI 836880 (mg)	N of patients treated	N of patients with DLTs during MTD evaluation period
360	6	1
720	3	2

Table 7.1.2: 2 Preliminary data from 1381-0001

Dose BI 754091 (mg)	N of patients treated	N of patients with DLTs during MTD evaluation period
80	3	0
240	34	0
400	3	0

Table 7.1.2: 3 Preliminary data from 1381-0004

Dose BI 754091 (mg)	N of patients treated	N of patients with DLTs during MTD evaluation period
240	6	0

Table 7.1.2: 4 Hypothetical data expected from 1336-0011

Dose BI 836880 (mg) / BI 754091 (mg)	N of patients treated	N of patients with DLTs during MTD evaluation period
360 / 240	1	1
500 / 240	0	0
720 / 240	0	0

The following steps were performed to derive the prior distribution for Part 2:

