- 1) The meta-analytic predictive prior was derived for both compounds and for the interaction parameter η using the information in Tables 7.1.2: 1 – 7.1.2: 4, allowing for moderate to substantial between-trial heterogeneity, tau parameters are assumed to be normally distributed with mean $\log(0.25)$ and SD $\log(2)/1.96$. See a reference ([R18-3210](#)) for details on the MAP prior. These prior components were assigned 90% mixture weight for both compounds.
- 2) A second, weakly informative prior component was added with the same mean values as the MAP prior, standard deviation (2, 1) and correlation 0. This mixture component was assigned 10% mixture weight

The resulting parameters of the prior distributions for four combination levels, i.e., (120/240, 360/240, 500/240, 720/240), are given in [Table 7.1.2: 5](#). The corresponding prior probabilities of a DLT at different dose combinations and the corresponding probabilities of under toxicity, targeted toxicity and over toxicity are shown in [Table 7.1.2: 6](#). As can be seen from Table 7.1.2: 6, the dose combination 120 mg BI 836880 and 240 mg BI 754091 has prior probability of over toxicity below 25%. It fulfils the overdose criterion and is therefore a suitable starting dose combination.

Table 7.1.2: 5 Prior Distribution

Parameter	Prior distributions Means, standard deviations, correlation	Mixture weight
log(α_1), log(β_1): component 1	(-1.877,-0.574), (0.983, 0.893), -0.145	0.9
log(α_1), log(β_1): component 2	(-1.877,-0.574), (2,1), 0	0.1
log(α_2), log(β_2): component 1	(-1.500, 1,213), (1.070, 1.034), 0.387	0.9
log(α_2), log(β_2): component 2	(-1.500, 1,213), (2,1), 0	0.1
η	0.466, 0.989	N/A

Table 7.1.2: 6 Prior probabilities of DLTs

Dose (mg)	Dose (mg)	Probability of true DLT rate in			Descriptive statistics				
		[0,0.16)	[0.16,0.33)	[0.33,1]	Mean	SD	2.5%	50%	97.5%
BI 836880	BI 754091								
120	240	0.486	0.327	0.187	0.209	0.162	0.023	0.165	0.637
360	240	0.280	0.311	0.409	0.318	0.213	0.035	0.273	0.814
500	240	0.134	0.213	0.653	0.468	0.255	0.059	0.454	0.933
720	240	0.077	0.100	0.822	0.680	0.299	0.065	0.774	1.000

The prior will be updated once the trial has started in case new data that can be used will be available. The prior that is used for each BLRM analysis for the SMC meetings will be documented in the SMC minutes, the prior used for the final analysis will be documented in the TSAP.

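### The Part II prior in Table 7.1.2:5 conflicts with its own source data for BI 754091 (0 DLTs in 46 patients) and with the overdose probabilities in Table 7.1.2:6.

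*Protocol*

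**What the plan says.** All references are to protocol section 7.1.2 unless stated.

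- **Source of the prior.** Step 1 of the prior derivation states that the MAP prior for both compounds and for the interaction was derived "using the information in Tables 7.1.2: 1 – 7.1.2: 4, allowing for moderate to substantial between-trial heterogeneity". It carries 90% weight for each drug. Step 2 adds a 10% component "with the same mean values as the MAP prior, standard deviation (2, 1) and correlation 0".
- **BI 754091 data.** "Table 7.1.2: 2 Preliminary data from 1381-0001" lists 0/3 at 80 mg, 0/34 at 240 mg and 0/3 at 400 mg. "Table 7.1.2: 3 Preliminary data from 1381-0004" lists 0/6 at 240 mg. Only Tables 7.1.2:1 (Part I) and 7.1.2:4 (1336-0011) are titled hypothetical.
- **Reference doses.** 500 mg and 240 mg "are set for BI 836880 and BI 754091, respectively".
- **Printed prior, Table 7.1.2:5, component 1** (means of log alpha and log beta; SDs; correlation). BI 836880: (-1.877, -0.574); (0.983, 0.893); -0.145. BI 754091: (-1.500, 1.213); (1.070, 1.034); 0.387. The interaction has mean 0.466 and SD 0.989.
- **Printed consequence, Table 7.1.2:6.** The prior probability of a DLT rate of 0.33 or more is 0.187, 0.409, 0.653 and 0.822 at 120, 360, 500 and 720 mg BI 836880 with 240 mg BI 754091. The text concludes that 120/240 meets the 25% criterion and is a suitable start.

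**The concern.** At a drug's reference dose the log dose ratio is zero, so the inverse logit of mean log(alpha) is the prior median DLT rate there. The weak component shares the same mean, so this holds for the whole mixture. A drug with no DLT in 40 patients at 240 mg should not come out of a fit to those data with a median of 13% or more.

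The Part II model adds the two drugs' toxicity and applies the EWOC limit to the result. Toxicity wrongly charged to BI 754091 therefore raises the overdose probability of every combination. If the rows are also attached to the wrong drugs, a reader cannot tell which prior produced the overdose figures, the data scenarios or the operating characteristics. The combination MTD, a primary endpoint of Part II, rests on this model.

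**Working it through.** **1. Median implied for BI 754091 alone at 240 mg.**
- As labelled: 1/(1 + e^1.500) = 18.2%.
- Rows exchanged: 1/(1 + e^1.877) = 13.3%.
- Data: 3 + 34 + 3 + 6 = 46 patients, 0 DLTs; at 240 mg 34 + 6 = 40, 0 DLTs. Exact one-sided 95% upper bound: 1 - 0.05^(1/40) = 7.2%.
- Chance of 0/40: (1 - 0.133)^40 = 0.003, or (1 - 0.182)^40 = 0.0003. Averaged over the spread of the printed priors it is 6.4% or 4.4%.

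**2. Reproducing Table 7.1.2:6.** I drew 2 million times from the Table 7.1.2:5 mixtures through the protocol's model: p0 = p1 + p2 - p1·p2, with the odds of p0 multiplied by exp(eta × d1/500 × d2/240). The printed 1,213 was read as 1.213.

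| Prior P(DLT rate ≥ 0.33) | 120/240 | 360/240 | 500/240 | 720/240 |
|---|---|---|---|---|
| Printed in Table 7.1.2:6 | 0.187 | 0.409 | 0.653 | 0.822 |
| Rows as labelled | 0.422 | 0.592 | 0.651 | 0.701 |
| Rows exchanged | 0.185 | 0.404 | 0.651 | 0.823 |
| Exchanged, BI 754091 refitted | 0.025 | 0.184 | 0.514 | 0.768 |

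Only the exchanged rows reproduce the table. They also reproduce Table 10.5.2:1: scenario 1 at 360/240, 0.253 against 0.248; scenario 5, 0.293 against 0.295; scenario 6, 0.605 against 0.602.

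**3. Refitting BI 754091.** The hyperprior is not printed. I assumed log(alpha) ~ N(logit 0.33, 1), log(beta) ~ N(0, 1) and log-normal tau with median 0.25. These settings reproduce the Part I MAP row in Table 7.1.1:2: (-2.26, 0.11); (0.677, 0.94); -0.07, against (-2.263, 0.116); (0.677, 0.946); -0.076. Applied to Tables 7.1.2:2 and 7.1.2:3 at 240 mg they give (-2.99, -0.20); (0.68, 0.92); -0.04. The median is 4.8 to 4.9% and the 97.5% quantile 15%.

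Sensitivity: hyperprior centres from 5 to 50%, SDs from 1 to 3 and tau medians of 0.25 or 0.5 gave medians between 0.4 and 7.7%. A joint fit that includes the 1/1 DLT of Table 7.1.2:4 gave 1.6%. Section 4.1.2.2 describes only 3 + 8 = 11 patients at 240 mg in 1381-0001; using 11 instead of 34 gave 7.4%. Reaching 13% took a tau median of 1.0, four times the stated value, with a 50% centre.

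**4. Effect on EWOC (limit 0.25), exchanged rows, only BI 754091 refitted.**

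| Data | Level | Before | After | EWOC outcome |
|---|---|---|---|---|
| None | 360/240 | 0.404 | 0.184 | changes |
| 1/6 at 120/240 | 360/240 | 0.35 | 0.22 | changes |
| Scenario 2: 1/3 at 120/240 | 360/240 | 0.50 | 0.29 | same |
| Scenario 3: 2/3 at 120/240 | 120/240 | 0.528 (printed) | 0.26–0.28 | same |
| Scenario 4: 0/3 at 120/240, 0/3 at 360/240 | 500/240 | 0.388 | 0.353 | same |
| Scenario 4 | 720/240 | 0.69 | 0.69 | same |
| Scenario 5: 0/3, then 1/3 at 360/240 | 360/240 | 0.293 | 0.185 | changes |
| Scenario 6: 0/3, then 2/3 at 360/240 | 360/240 | 0.605 | 0.47–0.48 | same |

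Scenario 1 already permits 360/240 in the printed table. Of the six printed scenarios, only scenario 5 changes.

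**5. Why the upper levels stay blocked.** In the exchanged arrangement BI 836880 takes the row (-1.500, 1.213), which gives a median DLT rate of about 48% at 720 mg alone. Table 7.1.1:1 has 0/17 at that dose, and the dummy Part I data add 2/3. With both drugs re-derived, 500/240 in scenario 4 falls to about 0.17 to 0.20.

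**The case against.** **The printed prior is provisional.** Section 7.1.2 says that dummy data will be replaced, all available information used at each run, and the resulting prior documented. This stands in part: a reader might infer that the error runs on into live dose decisions, and the documents do not show that. It could lie in the code or only in the transcription. However, the BI 754091 tables are not among the dummy data, so replacing the dummy data does not by itself repair this component.

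**Escalation is not generally blocked.** A reader might infer that the BI 754091 prior closes off 500/240 and 720/240. It does not: with that row alone corrected, both still fail in scenario 4. A downward bias in the combination MTD is plausible but was not simulated.

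**The starting dose.** The 0.42 at 120/240 might be read as showing that the start breaches EWOC. It shows only that the labels and Table 7.1.2:6 disagree. The exchanged rows give 0.185, and the refits give lower values.

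**Cause.** Fitting the BI 754091 data at a 500 mg reference dose gives (-1.55, 1.32); (1.03, 0.93); 0.50, near the printed row but not a reproduction of it. That explanation is conjecture.

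**Table 7.1.1:1.** Step 1 does not name it, which might suggest that 1336-0001 was left out. The section says that the trial is incorporated and points to the table. With the settings above, fitting BI 836880 at 500 mg gives a mean log(alpha) of -1.89 with that table and -0.67 without it; the row labelled BI 836880 has -1.877. This is probably a citation slip.

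**Conclusion.** Wrong as written. Table 7.1.2:5 cannot be reconciled with the BI 754091 data under the stated heterogeneity and any plausible hyperprior tried: a median of 13.3 or 18.2% at 240 mg, against about 5% on refitting (range 0.4 to 8%). As labelled, it also does not yield Table 7.1.2:6, which needs the two drugs' rows exchanged.

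In the exchanged arrangement, correcting BI 754091 alone takes the prior overdose probabilities to about 0.03/0.18/0.51/0.77. EWOC outcomes change around 360/240. The block at 500/240 and 720/240 comes mainly from the row then used for BI 836880. The error overstates toxicity and is conservative for patients; the cost is unreliable escalation guidance and unreliable operating characteristics.

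The implied medians and the mismatch between the two tables follow from printed figures. The refitted values rest on assumed hyperpriors, although the direction did not change in any plausible setting tried. Which row belongs to which drug cannot be settled from the documents.

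**What to change.** 1. State which row of Table 7.1.2:5 belongs to which drug, and which arrangement was used for Tables 7.1.2:6 and 10.5.2:1–3.
2. Re-derive the BI 754091 component from Tables 7.1.2:2 and 7.1.2:3 at 240 mg. Re-derive the BI 836880 component from Tables 7.1.1:1 and 7.1.2:1 (or the actual Part I data) at 500 mg.
3. Print the hyperpriors for the means, and name Table 7.1.1:1 in step 1.
4. Check each component against its source data, for example by the predictive probability of 0/40 at 240 mg for BI 754091.
5. Re-issue Tables 7.1.2:5, 7.1.2:6 and 10.5.2:1–3 before the first Part II model run, and record the corrected prior in the SMC minutes and the TSAP, as section 7.1.2 already requires.
6. Reconcile the statement about the starting combination in section 7.1.2 with the corrected tables. That is for the sponsor; no dose is proposed here.

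The cost is a re-run of existing code and replacement of tables. No patients or new data are needed.

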where $r_{d1,d2}$ denotes the variable describing the observed number of DLTs from $n_{d1,d2}$ patients at the dose combination d_1, d_2 .

Since a Bayesian approach is applied, prior distributions f for each of the parameter vectors $\theta_1 = (\log(\alpha_1), \log(\beta_1))$, $\theta_2 = (\log(\alpha_2), \log(\beta_2))$ and for the interaction term η need to be specified.

The prior distributions for θ_1 and θ_2 will be specified as mixtures of two multivariate normal distributions, i.e.

$$f(\theta_k) = a_{1,k} f_1(\theta_k) + a_{2,k} f_2(\theta_k)$$

with

$a_{1,k}, a_{2,k}$ the prior mixture weights, $k=1,2$ and

$$f_i(\theta_k) = \text{MVN}(\mu_{ik}, \Sigma_{ik}) \quad (k=1,2),$$

the multivariate normal distribution of the i -th component with mean vector μ_{ik} and covariance matrix Σ_{ik} , where

$$\Sigma_{ik} = \begin{pmatrix} \sigma_{ik,11}^2 & \sigma_{ik,11}\sigma_{ik,22}\rho_{ik} \\ \sigma_{ik,11}\sigma_{ik,22}\rho_{ik} & \sigma_{ik,22}^2 \end{pmatrix}$$

Mixture prior distributions have the advantage that they allow for specification of different logistic dose-toxicity curves, therefore making the prior more robust.

A meta-analytic approach will be used for the prior specification of η .

The estimated probability $\pi_{12,d1,d2}$ of a DLT at each dose combination d_1, d_2 from the model will be summarised using the following intervals:

Under dosing: [0.00, 0.16)

Targeted toxicity: [0.16, 0.33)

Over dosing: [0.33, 1.00]

The BLRM-recommended dose for the next cohort is the level with the highest posterior probability of the DLT rate falling in the target interval [0.16, 0.33) among the doses fulfilling EWOC. Applying the EWOC criterion it should be unlikely (<25% posterior probability) that the DLT rate at that dose will exceed 0.33.

As described The MTD may be considered to be reached if one of the following criteria is fulfilled:

1. The posterior probability of the true DLT rate in the target interval [0.16 – 0.33) of the MTD is above 0.5, OR
2. At least 9 patients have been treated in the study, of which at least 6 at the MTD.

Prior derivation:

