10.5.2 Part II (BI 836880 and BI 754091 combination dose finding)

Hypothetical data scenarios

Hypothetical data scenarios are shown in [Table 10.5.2: 1](#). These scenarios reflect potential on-study data constellations and related escalation as allowed by the model. For each scenario, the probability of overdose for the current dose combination, as well as the next potential dose combination and related probabilities of under-dosing, target dose, and over-dosing are shown.

Table 10.5.2: 1 Hypothetical data scenarios

Scenario	Dose (mg)	# DLT	# Pat	Current Dose: P(OD)	Next Recommended Dose	Next Dose		
						P(UD)	P(TD)	P(OD)
1	120/240	0	3	0.054	360/240	0.413	0.339	0.248
2	120/240	1	3	0.228	120/240	0.336	0.436	0.228
3	120/240	2	3	0.528	NA	NA	NA	NA
4	120/240	0	3					
	360/240	0	3	0.085	360/240	0.609	0.306	0.085
5	120/240	0	3					
	360/240	1	3	0.295	120/240	0.627	0.324	0.049
6	120/240	0	3					
	360/240	2	3	0.602	120/240	0.408	0.440	0.152

For example, scenario 1 represents the case that no DLT is observed in the first three patients at the starting dose combination of 120/240 mg/kg. In this case, the next optimal dose combination, i.e. the dose combination with the highest probability of being in the target interval, is the next dose combination, i.e., 360/240 mg/kg. Scenarios 5 illustrates the case where low dose combination cohorts have no DLT and the highest dose combination level 360/240 mg/kg has 1 DLT, in such cases, BLM would de-escalate and put patients on 120/240 mg/kg. In scenarios 3, two DLT is observed already in the patient. In this case, the model recommends stopping the trial because of high overdose probabilities.

Operating characteristics

Operating characteristics are a way to assess the long-run behaviour of a model by illustrating the precision of the design in estimating the MTD. Under an assumed true dose-toxicity curve, metrics such as the probability of recommending a dose combination with true DLT rate in the target interval can be approximated via simulation. [Table 10.5.2: 2](#) describes 5 assumed true dose-toxicity scenarios which were used to assess the operating characteristics of the model. These scenarios reflect a wide range of possible cases as follows:

- Scenario 1: aligned with prior means
- Scenario 2: high-toxicity scenario
- Scenario 3: low-toxicity scenario
- Scenario 4: non-logistic dose-toxicity scenario
- Scenario 5: low-toxicity followed by high-toxicity
- Scenario 6: super high-toxicity scenario

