7.4 PRIMARY ENDPOINT

In part I and II, the primary endpoint is to assess the MTD based on the number of patients presenting DLTs during the MTD evaluation period. The primary analysis is for the determination of the MTD. The purpose of this analysis is to summarize and document the data that led to the selection of the MTD. Therefore, an overall summary of DLTs (see CTP Section 4.1.7 for the definition of DLTs) which occurred during the MTD evaluation period will be provided for each dose cohort from the dose finding cohort treated set. Patients, if any, who did not complete the MTD evaluation period for reasons other than DLT will be excluded from the analysis of the primary endpoint.

A summary of the number of patients with DLTs overall in any cycle will be also given by initial treatment and displayed in a similar format to the summary of DLTs occurring in the MTD evaluation period.

The analysis of the MTD is based on a Bayesian logistic regression model (BLRM) guided by the escalation with overdose control principle. The MTD is defined as the highest dose for a given schedule that is expected to cause less than 25% risk of the true DLT rate being above or equal to 33% during the MTD evaluation period. Estimation of the MTD during the dose escalation phase of the study will be based upon the estimation of the posterior probability of the incidence of DLT in toxicity categories during the MTD evaluation period for all evaluable patients. The model to be used is specified in CTP Section 7.

The posterior probabilities that the toxicity rates of each dose level fall into the categories specified in CTP Section 7 will be displayed.

[figure not shown]

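### Protocol Tables 7.1.2:5 and 7.1.2:6 contradict each other: the Part II prior as labelled gives 120/240 mg an overdose probability of 0.42, not the printed 0.187

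*Protocol*

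**What the plan says.** Protocol 7.1.2 models Part II with a five-parameter logistic model in which index 1 is BI 836880 and index 2 is BI 754091. The reference doses of 500 mg and 240 mg "are set for BI 836880 and BI 754091, respectively".

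Table 7.1.2:5 gives the prior by index. Component 1 for index 1 is printed, after its opening minus sign, as "1.877,-0.574), (0.983, 0.893), -0.145"; for index 2, likewise, as "1.500, 1,213), (1.070, 1.034), 0.387". Table 7.1.2:6 is presented as the DLT probabilities that correspond to this prior.

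The overdose rule is: "Applying the EWOC criterion it should be unlikely (<25% posterior probability) that the DLT rate at that dose will exceed 0.33". From Table 7.1.2:6 the text concludes that "the dose combination 120 mg BI 836880 and 240 mg BI 754091 has prior probability of over toxicity below 25" per cent, and that this combination is therefore suitable as a start.

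On the dummy data behind the prior, 7.1.2 says: "This dummy data will be replaced by actual data as soon as it becomes available". SAP 7.4 prints no prior of its own and refers back: "The model to be used is specified in CTP Section 7".

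**The concern.** Table 7.1.2:6 should be a direct consequence of Table 7.1.2:5 and the model. If it is not, the parameters shown to the reader are not those that produced the overdose probabilities, and the stated reason for accepting the starting combination cannot be confirmed from the protocol.

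The same model guides every Part II dose step and the MTD estimate. The two drugs have very different prior slopes: the mean of log(β) is −0.574 in one row and 1.213 in the other. An exchange of rows therefore changes how steeply risk rises with the BI 836880 dose, and with it which combinations are admissible after given data.

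**Working it through.** **Inputs** (Protocol 7.1.2 and Table 7.1.2:5)
- Index 1: means (−1.877, −0.574). Component 1 (weight 0.9) has SDs (0.983, 0.893) and correlation −0.145.
- Index 2: means (−1.500, 1.213), the printed comma read as a decimal point. Component 1 (weight 0.9) has SDs (1.070, 1.034) and correlation 0.387.
- Component 2 (weight 0.1) for each index: same means, SDs (2, 1), correlation 0.
- η: mean 0.466, SD 0.989.
- d1* = 500 mg, d2* = 240 mg; overdose means a DLT rate in [0.33, 1].

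**Model.** logit(πk) = log(αk) + βk·log(dk/dk*); π0 = π1 + π2 − π1π2; odds(π12) = odds(π0)·exp(η·(d1/d1*)·(d2/d2*)).

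**Check of the method.** The same sampler applied to the Part I prior (Table 7.1.1:2) gives overdose probabilities of 0.027 and 0.081 at 360 and 720 mg, against the printed 0.026 and 0.080.

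**Hand check at 120/240, all parameters at their means.** log(120/500) = −1.427 and exp(0.466 × 0.24) = 1.118.
- As labelled: β1 = exp(−0.574) = 0.563; logit π1 = −1.877 − 0.804 = −2.681, so π1 = 0.064. π2 = expit(−1.500) = 0.182. π0 = 0.235, odds 0.307 × 1.118 = 0.343, DLT rate 0.256.
- Rows exchanged: β1 = exp(1.213) = 3.364; logit π1 = −1.500 − 4.800 = −6.300, so π1 = 0.002. π2 = expit(−1.877) = 0.133. π0 = 0.134, odds 0.155 × 1.118 = 0.174, DLT rate 0.148.

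The printed median is 0.165. The plug-in value is not the median, but it already shows which version lies near the table.

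**Full prior, Monte Carlo (millions of draws)**

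| BI 836880 / BI 754091 (mg) | Overdose: printed | As labelled | Exchanged | Median: printed | As labelled | Exchanged |
|---|---|---|---|---|---|---|
| 120/240 | 0.187 | 0.422 | 0.185 | 0.165 | 0.288 | 0.163 |
| 360/240 | 0.409 | 0.592 | 0.404 | 0.273 | 0.392 | 0.271 |
| 500/240 | 0.653 | 0.651 | 0.651 | 0.454 | 0.453 | 0.453 |
| 720/240 | 0.822 | 0.701 | 0.823 | 0.774 | 0.546 | 0.776 |

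Over all 32 entries (three interval probabilities, mean, SD and three quantiles at four levels), 23 differ from print by more than 0.01 as labelled, with a largest difference of 0.26. With the rows exchanged the largest difference is 0.005. The 500/240 row cannot discriminate: both drugs are then at their reference doses and the model is symmetric in the two rows.

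**Other readings tested.** With the labelled rows: component 1 only, SDs read as variances, no interaction, negative η, β on the linear scale, sign changes of the log(β) means, and d1* = 720 mg. These leave overdose at 120/240 between 0.33 and 0.72. Exchanging the dose columns instead gives 0.139 there but does not reproduce the table. Among all 32 full or partial exchanges of the two rows' parameters, the full exchange fits best; the nearest partial one misses by 0.012, and every one that leaves the log(β) means in place misses by more than 0.2.

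**Second table.** Current-dose overdose probabilities in Table 10.5.2:1, scenarios 1 to 6, with posteriors by importance weighting:

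| | 1 | 2 | 3 | 4 | 5 | 6 |
|---|---|---|---|---|---|---|
| Printed | 0.054 | 0.228 | 0.528 | 0.085 | 0.295 | 0.602 |
| Exchanged | 0.055 | 0.225 | 0.532 | 0.083 | 0.293 | 0.604 |
| As labelled | 0.160 | 0.422 | 0.724 | 0.134 | 0.380 | 0.681 |

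**Effect on dose steps (limit 0.25)**
- Before any data: as labelled, all four combinations exceed the limit.
- 0/3 at 120/240: overdose at 360/240 is 0.36 as labelled, 0.248 printed and 0.253 exchanged. The last two straddle the limit within simulation error.
- 1/3 at 120/240: overdose there is 0.422 as labelled, so nothing is admissible; it is 0.228 printed, and the table continues at 120/240.
- 0/3 at 120/240, then 2/3 at 360/240: overdose at 120/240 is 0.326 as labelled, so nothing is admissible; it is 0.152 printed (0.145 exchanged), and the table continues there.
- 0/3 at 120/240, then 0/3 at 360/240: overdose at 500/240 is 0.22 as labelled, within the limit, and 0.39 exchanged, outside it.

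**The case against.** The arithmetic is not in dispute; the objections concern weight.

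- **It is probably only a label.** Two output tables match the exchanged rows, and Table 7.1.2:5 identifies the drugs only by subscript. A labelling slip is the likelier cause, in which case 0.187 was calculated as intended. This stands as a likelihood. The documents do not exclude an exchanged drug assignment in the code, and then Tables 7.1.2:6 and 10.5.2:1, and probably Table 10.5.2:3, would describe the wrong model.
- **The prior is a placeholder.** Section 7.1.2 says the dummy data will be replaced and each prior recorded in the SMC minutes, with the final one in the SAP. This lowers the impact. It does not correct an exchanged assignment carried into later runs.
- **The last dose step above is not a change of recommendation.** After 0/3 and 0/3, both versions recommend 360/240: as labelled, its target-interval probability is 0.387 against 0.349 at 500/240. This is right. What differs is the set of permitted doses, and Protocol 3.1 permits escalation to any dose that meets the overdose limit and the escalation rules, with the SMC deciding and trial 1336-0011 setting a cap.
- **The match is looser for next-dose figures.** In scenario 1, exchanged, underdosing at 360/240 is 0.401 against the printed 0.413. Simulation error may explain this, and it does not rescue the labelled rows.

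**Conclusion.** The concern holds. Tables 7.1.2:5 and 7.1.2:6 cannot both be right under the stated model, and the stated justification of the starting combination fails under the prior printed beside it (0.42 against a limit of 0.25). Of the readings tested, only a full exchange of the two drugs' rows reproduces the printed results; this is strong evidence but not proof that no other reading would.

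Neither version is uniformly more cautious: the labelled one is stricter at low doses and more permissive at 500/240 after clean cohorts. The result assumes the model and reference doses as written and 1.213 for the misprinted mean. That value has no effect as labelled, because BI 754091 is always at its reference dose, but it matters once the rows are exchanged. Nothing here says which table, or which dose, is correct. The point must be fixed because it concerns the overdose safeguard of Part II.

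**What to change.** 1. Trace both rows of Table 7.1.2:5 to the code that was run, and confirm each drug's parameters and reference dose.
2. State which data entered the fit. Section 7.1.2 says trial 1336-0001 is incorporated, but step 1 of the derivation names only Tables 7.1.2:1 to 7.1.2:4, which do not contain it.
3. While tracing, check two plausibility points, which are not asserted as errors. The prior median DLT rate for BI 754091 at 240 mg is 18% as labelled and 13% exchanged, against 0/40 observed (34 + 6 in Tables 7.1.2:2 and 7.1.2:3; two-sided 95% upper limit 1 − 0.025^(1/40) = 8.8%). The prior mean DLT rate for BI 836880 720 mg alone is 22% as labelled and 51% exchanged, against 0/17 in trial 1336-0001 and the dummy 2/3.
4. Regenerate Tables 7.1.2:5, 7.1.2:6, 10.5.2:1 and 10.5.2:3 from one run, and correct the decimal comma.
5. Restate whether the starting combination meets the overdose criterion under that prior, reconcile the text, and have SAP 7.4 cite the corrected prior.

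The cost is a code trace, one re-run of existing programs and a protocol and SAP correction. No patients or procedures are added.
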